Initial visits during caffeine maintenance. On their first visit to the laboratory following screening, participants will review food and beverage restrictions, provide a saliva sample, and receive a food diary. The food diary is used to monitor food and beverage consumption during the first week of each condition to assist in adhering to the dietary restrictions. During this visit, participants will also receive study capsules in blister packs and ingest their first dose with water. Participants will receive instructions to take a single dose three times per day at the same times every day. The study team will send reminders to take the study medication at the appropriate time via email or text message or via medication timers supplied to the participant during the study. The times at which participants are instructed to take the study medication will be approximately 2 hours before and 3 and 8 hours after they will attend the laboratory for experimental sessions (see *Experimental Sessions* below). For example, a participant planning to attend experimental sessions at 9 AM would take a study capsule containing 200 mg of caffeine (absolute dose) every day at 0700 h, 1200 h, and 1700 h. This caffeine maintenance schedule is roughly equivalent to 12 oz of brewed coffee three times daily (Sweeney et al., 2018). Given this dosing schedule, experimental sessions will be limited to the morning hours to minimize the sleep disruptive effects of caffeine. Participants will attend a second initial session during the first week of the caffeine maintenance during which they will provide a saliva sample and review their food and beverage diary with study staff.

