Experimental sessions during caffeine maintenance. After receiving caffeine maintenance for at least one week, participants will continue daily caffeine administration and will also be exposed to experimental test sessions across approximately 3-4 weeks (one session each for placebo, 1, 2, 3 and 4 mg/70 kg nicotine and 300 mg caffeine). The purpose of the nicotine sessions is to assess the subjective and reinforcing effects of nicotine, whereas the purpose of the caffeine session is as a manipulation check to test tolerance to caffeine during caffeine maintenance relative to placebo maintenance. The order in which the different doses for experimental sessions are received will be counterbalanced across participants. Subjects will report to the laboratory approximately 2-3 times per week, depending on schedule considerations. Sessions will be separated by at least 48 hours (e.g., Monday, Wednesday, Friday sessions). At each visit, participants will provide a saliva sample, complete pre-drug subjective questionnaires, and orally ingest study capsules with water under double-blind conditions. After leaving the laboratory, outcome measures will be assessed at 1, 2, 3, and 4 hours post-capsule administration.

Measures will include subjective ratings of drug effects (e.g., energetic, drowsy/sleepy, elated, jittery/shaky) and surrogate measures of reinforcement such as liking, take again, and the multiplechoice reinforcement procedure, which we have used in previous research. These questionnaires will be completed online using Qualtrics survey technology, including via the Qualtrics App while in the laboratory, or using conventional paper forms. When participants are completing their surveys online, a survey link will be sent to them via email or text message. Paper forms of surveys will be provided as a back-up in the event of technical issues with administering surveys via Qualtrics, in the event of difficulties with participant compliance for online assessments, or in the event the participant does not have a smart phone or computer access. The multiple-choice procedure will assess participant preference for "today's drug" over various amounts of money ranging from -\$30 (i.e., forego \$30 rather than receive "today's drug") to \$30 (i.e., receive \$30 rather than receive "today's drug").

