Final visit. Participants will return to the laboratory to receive their bonus payment for study completion so that we have the opportunity to review their subjective drug effects from the multiplechoice reinforcement session and discuss with them if necessary. They will also complete an end-ofstudy questionnaire which will assess their beliefs about what conditions they may have experienced during the study and any perceived differences between conditions.

Measures

Screening/Descriptive Measures: The following measures will be administered at study screening, the online self-screener or online preliminary screening in order to establish patient eligibility and characterize the sample. Basic demographic information and personality measures will be examined as potential covariates of individual differences in drug response following drug administration. The measures described will be administered via computer or using paper or pencil, and

as such formatting or question wording may change slightly to adjust for computer vs. paper administrations.

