Family Tree Questionnaire (FTQ). The Family Tree Questionnaire (FTQ) for Assessing Family History of Alcohol Problems (Mann, Sobell, & Sobell, 1985) is an instrument that allows participants to indicate each of their blood relative's alcohol use and categorize it according to their knowledge of their family members' problematic use (e.g., never drank, social drinker, possible problem drinker, definite problem drinker, don't know/don't remember). We have modified this questionnaire to include two additional modules allowing participants to categorize family members' known history of tobacco use and other drug use. It is possible that participants who show greater positive subjective drug response may have a greater number of relatives with problematic alcohol or drug use.

Experimental Session Measures: The following measures will be administered to participants before capsule administration at experimental test sessions (e.g., pre-drug subjective effects questionnaire) or at 1, 2, 3, or 4 hours after capsule administration. These questionnaires will be completed online using Qualtrics survey technology or using conventional paper forms. When

participants are completing their surveys online, a survey link will be sent to them via email or text message. Paper forms of surveys will be provided as a back-up in the event of technical issues with administering surveys via Qualtrics, in the event of difficulties with participant compliance for online assessments, or in the event the participant does not have a smart phone or computer access. Formatting or question wording may change slightly to adjust for computer vs. paper administrations.

COVID-19 Questionnaire. The same COVID-19 Questionnaire procedure (described above) will be administered prior to every in-person session to ensure safety for participants and research staff.

Subjective Effects Questionnaire. The Subjective Effects Questionnaire (SEQ) is an internally developed measure allowing participants to rate how they feel (e.g., energetic, drowsy/sleepy, elated, jittery/shaky) prior to ingesting the study drug and at 1, 2, 3, and 4 hours after capsule administration. Items on the subjective effects questionnaire were developed to detect effects of caffeine, nicotine, and stimulant drugs and we have successfully used the items in past research to detect significant drug dose effects (Duke et al., 2015; Sigmon & [name], 2011).

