Delay Discounting. The same brief delay discounting procedure (described above) may be administered during experimental test sessions at a single time point per session (e.g., 3 hrs after capsule administration) to probe for acute drug effects on decision-making.

Multiple-Choice Procedure. In the multiple-choice procedure, the subjective reinforcing value of the study drug dose is assessed by asking participants to indicate whether they would prefer to repeat "today's drug" or take placebo capsules and receive or lose money at the end of the study. The multiple-choice questionnaire asks participants make repeated choices between "today's drug" over various amounts of money ranging from -\$30 (i.e., forego \$30 rather than receive "today's drug") to \$30 (i.e., receive \$30 rather than receive "today's drug"). The multiple-choice questionnaire will only be administered at a single time point per session (e.g., 4 hrs after capsule administration). As has been done in previous studies (e.g., [name] et al., 1993; Zacny & Gutierrez, 2009), one of the participant's choices during the multiple-choice procedure will be randomly selected for reinforcement during a multiple-choice reinforcement session. If the selected choice was one of the study drugs, capsules containing selected study drug will be administered to the participant during the multiple-choice reinforcement session using the same procedures as in other experimental test sessions. If money was selected, then the amount of money chosen by the participant will be added or subtracted from the session payment and the participant will receive placebo capsules. Placebo capsules are administered if the choice was for money in order to make the procedures involved in choosing drug or money equivalent. This procedure has been successfully utilized in past research to determine and compare the subjective reinforcing value of administered drugs (Garrett & [name], 1998; [name] et al., 1996; [name] et al., 1993). We hypothesize that chronic caffeine may increase the subjective monetary value of nicotine.

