Both study drugs to be administered are legally marketed in the United States. Further, the study does not involve a route of administration, dose, or patient population that significantly increases the risk (or decreases the acceptability of the risk) associated with the use of the drug. Previous research has demonstrated that caffeine (Sigmon & [name], 2011) and nicotine (Duke et al., 2015) at the proposed doses (or indeed at higher doses) and the proposed route of administration (oral) are well-tolerated in non-drug-abusing volunteers. The maximum study dose of nicotine is consistent with what is currently available over-the-counter in oral form (e.g., 4 mg lozenges or gum). Caffeine is readily available over-the-counter in medications, supplements, beverages, and foods. The study is not intended to be reported to FDA in support of a new indication or to support any other change in labeling of the drugs. The study does not intended to promote or commercialize the drug products. As such, the proposed investigation is exempt from IND requirements because all of the criteria for an exemption in FDA regulations § 312.2(b) are met.

c. Justification and safety information if non-FDA approved drugs without an IND will be administered.

N/A

7. Study Statistics

a. Primary outcome variable.

Primary outcome measures will be participant ratings assessed pre-drug and at 1, 2, 3, and 4 hours post capsule administration during the experimental test sessions examining placebo, nicotine, and caffeine. Primary outcomes include subjective ratings (e.g. Subjective Effects Questionnaire, and surrogate measures of reinforcement such as liking, take again, monetary value). Primary outcomes will be compared within-subjects across the caffeine maintenance condition and the placebo maintenance condition.

b. Secondary outcome variables.

Secondary outcome measures will be subject demographic characteristics, drug use history, personality factors (e.g., sensation seeking), and decision-making factors (i.e., delay discounting) that will be examined as they correlate to positive subjective effects of nicotine during the experimental test sessions.

c. Statistical plan including sample size justification and interim data analysis.

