Subjective and reinforcing effects of nicotine (e.g., drug liking, take again, monetary value) will be examined as a function of nicotine dose and caffeine maintenance. Repeated measures ANOVAs will be conducted with caffeine maintenance phase (caffeine vs. placebo), drug dose (placebo and 4 doses of nicotine) and time (1, 2, 3, and 4 hours, as appropriate) as within-subjects factors. It is anticipated that there will be a significant drug dose by maintenance phase interaction such that positive subjective ratings on active nicotine sessions will be greater (and more differentiated from placebo) during the caffeine maintenance phase relative to the placebo maintenance phase. A sample size of 11 was previously sufficient to detect significant differences in nicotine reinforcement within subjects as a function of caffeine maintenance in an inpatient study (Jones & [name], 2003). In order to facilitate the exploration of effects of demographics (e.g., age, sex) and previous caffeine use, and to account for additional variability in an outpatient study, we propose a larger sample size of 36. This sample size is consistent with previous outpatient studies conducted by our laboratory that manipulated caffeine maintenance and examined differences in caffeine subjective effects (Evans & [name], 1992). The appropriateness of the proposed sample size is supported by a formal power analysis for repeated measures ANOVA examining an interaction between drug dose (five observations: placebo and four doses of nicotine) and caffeine maintenance (two levels treated as groups in the power analysis, thus conservatively assuming no correlation for this within-subjects factor) assuming an effect size of .20, correlation among repeated measurements of .5, desired power of .8, and $\alpha = .05$.

It is anticipated that in order to have 36 participants successfully complete the study, approximately 60 participants may have to be enrolled in order to allow for the possibility of participant dropout (i.e., attrition of up to 40% of enrolled participants). In order to obtain 60 enrolled participants, we anticipate that as many as 150 individuals may need to be consented and screened for study eligibility during the in-person Screening session (i.e., a screening failure rate of approximately 60%).

d. Early stopping rules.

There are no early stopping rules in this study.

8. Risks

a. Medical risks, listing all procedures, their major and minor risks and expected frequency.

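### The pre-drug Subjective Effects Questionnaire score has no role in the section 7c ANOVA; using it as a session-level covariate in the dose × maintenance phase test would be a cheap, optional gain in precision

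*Combined protocol and SAP*

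**What the plan says.** Section 7a (primary outcome variable) states: "Primary outcome measures will be participant ratings assessed pre-drug and at 1, 2, 3, and 4 hours post capsule administration". It names the SEQ, liking, take again and monetary value as examples.

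Section 7c (statistical plan) specifies repeated measures ANOVAs with maintenance phase, drug dose (placebo and four nicotine doses) and "time (1, 2, 3, and 4 hours, as appropriate) as within-subjects factors". The predicted result is a dose × phase interaction. The section names no covariate and no pre-drug time level.

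Section 4a shows which measures have a pre-drug value:
- **SEQ.** Items are rated "prior to ingesting the study drug and at 1, 2, 3, and 4 hours after capsule administration". The description of the experimental sessions agrees: "At each visit, participants will provide a saliva sample, complete pre-drug subjective questionnaires, and orally ingest study capsules with water".
- **Monetary value.** The multiple-choice questionnaire is given once per session, with 4 hours after the capsule as the example.
- **Liking and take again.** No pre-drug rating is documented.

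The covariates that section 4a does mention are participant characteristics: "Basic demographic information and personality measures will be examined as potential covariates of individual differences in drug response". Delay discounting at screening is treated in the same way. The pre-drug SEQ score is not among them.

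Maintenance capsules are scheduled "approximately 2 hours before and 3 and 8 hours after they will attend the laboratory for experimental sessions".

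**The concern.** Each participant is compared with himself or herself, so stable differences between people in how they rate the SEQ already drop out. Differences between one person's own sessions do not. A participant may arrive rested on one day and tired on another. If that state carries into the ratings at hours 1 to 4, it adds noise to the dose × phase comparison. The trial measures this state before every session capsule, but section 7c does not use it. Section 7c itself cites the additional variability of an outpatient study as one reason for the larger sample.

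What is at stake is the width of the confidence intervals for SEQ items. The validity of the dose × phase test is not in question. A stated role for the pre-drug score would also remove a choice that could otherwise be made after the data are seen.

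**Working it through.** **Inputs from section 7c.** N = 36 completers; 5 dose levels; 2 maintenance phases; effect size .20, read here as Cohen's f; correlation among repeated measurements ρ = .5; α = .05; target power .80. Sphericity is assumed.

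**Assumed input.** r is the within-person, session-level correlation between the pre-drug score and the post-dose rating. The documents do not give it. The .5 in section 7c is the correlation among repeated measurements across doses, which is a different quantity. The values .2, .3 and .5 are illustrative, with r = 0 as the floor.

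**1. The plan's own power calculation.** Section 7c describes it as "two levels treated as groups in the power analysis, thus conservatively assuming no correlation for this within-subjects factor". With two groups:
- λ = f² × N × 5 / (1 − ρ) = .04 × 36 × 5 / .5 = 14.4
- df = 4 and (36 − 2) × 4 = 136
- power = .864

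The same inputs reach .80 at N = 32 (power .814). They therefore support 36, which is all that section 7c claims.

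**2. The analysis actually planned, with phase within subjects.** Taking ρ = .5 among all ten sessions:
- λ = .04 × 36 × 10 / .5 = 28.8
- df = 4 and (36 − 1) × 4 = 140
- power = .995

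**3. Adding the pre-drug score as a covariate.** The error variance is multiplied by 1 − r², the interval width by √(1 − r²), and λ is divided by 1 − r². One error degree of freedom is lost.

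| r (assumed) | 1 − r² | Variance reduction | √(1 − r²) | Interval narrower by | Power, two-group (λ; df 4, 135) | Power, fully within (λ; df 4, 139) |
|---|---|---|---|---|---|---|
| 0 | 1.00 | 0% | 1.000 | 0% | .8637 (14.4) | .9949 (28.8) |
| .2 | .96 | 4% | .980 | 2% | .879 (15.0) | .9962 (30.0) |
| .3 | .91 | 9% | .954 | 5% | .897 (15.8) | .9975 (31.6) |
| .5 | .75 | 25% | .866 | 13% | .950 (19.2) | .9996 (38.4) |

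At r = 0 the lost degree of freedom costs about .0001 in the two-group calculation (.8638 to .8637) and nothing visible to four decimals fully within subjects.

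The precision gain can also be put as the smallest f detectable with 80% power in the fully within-subject analysis. It is .131 unadjusted, and .128, .125 and .113 at r = .2, .3 and .5.

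**4. Validity of the adjusted dose × phase test.** A simulation used 36 participants, 5 doses × 2 phases, four hourly ratings averaged per session, a pre-drug mean shifted by .5 SD between phases, and 6,000 runs per setting. Type I error of the adjusted test was .052, .050, .049 and .050 at r = 0, .2, .3 and .5. A second simulation (3,000 runs) gave the same average interaction estimate with and without adjustment (.398 and .398 at r = .3). The ratio of standard errors was .956, in line with the .954 in the table.

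**5. The maintenance main effect.** The pre-drug score is taken about 2 hours after a maintenance capsule, so maintenance can itself change it. In the second simulation maintenance shifted the pre-drug score by .5 SD, and the maintenance effect on the outcome was .50. At r = .3 adjustment removed .3 × .5 = .15, leaving .35. The adjusted main effect thus answers a different question from the unadjusted one.

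**The case against.** The strongest reply is that this is a preference. A within-subject ANOVA without a session-level covariate is valid, participant blocking already removes between-person differences, and power is about .995 at the plan's effect size. The size of the gain rests entirely on an r that the documents do not supply. The larger-looking power gain, from .864 to between .879 and .950, belongs to the two-group calculation. Section 7c calls that calculation conservative, and it is not the planned analysis. All of this stands, and it is why the point is optional.

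Three further points limit the scope, and they also stand. The measures that section 7c gives as examples are liking, take again and monetary value, and none of them is affected. The calculations cover the dose × phase test only; the dose main effect has its own error term, and no gain has been shown for it. Finally, a model on session averages over hours 1 to 4 drops the planned time factor, which must then be kept elsewhere.

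A reader might also infer more than the documents support:
- **That sections 7a and 7c contradict each other, with a primary endpoint left out of the analysis.** Section 7a can be read simply as the assessment schedule. It groups several measures, and at least one of them, monetary value, has no pre-drug rating.
- **That the omission biases the result or leaves the trial underpowered.** It does neither.
- **That ratings will be analysed as change from the pre-drug score.** No passage proposes this.

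None of this gives a reason against using a measurement that is already collected before each session capsule and that costs one degree of freedom.

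**Conclusion.** The point holds as an optional improvement for SEQ items in the dose × phase test. The pre-drug SEQ score is collected at every experimental session and has no stated role in the analysis. Using it would narrow intervals by about 2% to 13% if r lies between .2 and .5, and by nothing if r is 0. Power at the plan's effect size would barely change. These figures assume that .20 is Cohen's f, that sphericity holds, that ρ = .5 applies among all ten sessions in the fully within-subject calculation, and that all 36 completers have complete data. Confidence is good on what the text says and on the validity of the adjusted test. It is low on the size of the gain, because r is unknown.

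**What to change.** In section 7c, for SEQ items only:

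1. State that the dose × maintenance phase test includes that session's pre-drug score as a session-level covariate. The outcome is the session average over hours 1 to 4; the model contains participant × phase, participant × dose, dose × phase and the covariate.
2. Keep the planned ANOVA with its time factor, both for the time effects and as the unadjusted sensitivity analysis.
3. Report the maintenance main effect unadjusted, and give the reason: the maintenance capsule taken about 2 hours before the session may already have moved the pre-drug score.
4. Leave liking, take again and monetary value as planned.

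The cost is a revised model statement, a second model for each SEQ item and one error degree of freedom. No new data are needed. If the sponsor prefers not to adjust, one sentence in section 7c saying that the pre-drug score is descriptive would at least settle its role.

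### The all-within-subjects ANOVA in section 7c has no analysis set or missing-data rule; as ordinarily run it discards usable ratings from participants with incomplete placebo or nicotine sessions

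*Combined protocol and SAP*

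**What the plan says.** Section 7c names the method: "Repeated measures ANOVAs will be conducted with caffeine maintenance phase (caffeine vs. placebo), drug dose (placebo and 4 doses of nicotine) and time". The same sentence goes on to make every factor within subjects: "drug dose (placebo and 4 doses of nicotine) and time (1, 2, 3, and 4 hours, as appropriate) as within-subjects factors". The power analysis in the same section covers the dose-by-phase interaction, with the phase factor's "two levels treated as groups in the power analysis, thus conservatively assuming no correlation for this within-subjects factor".

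On numbers, section 7c says "It is anticipated that in order to have 36 participants successfully complete the study, approximately 60 participants may have to be enrolled", which allows for "attrition of up to 40% of enrolled participants".

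On data collection, section 4a (Experimental sessions during caffeine maintenance) says: "After receiving caffeine maintenance for at least one week, participants will continue daily caffeine administration and will also be exposed to experimental test sessions". It continues: "After leaving the laboratory, outcome measures will be assessed at 1, 2, 3, and 4 hours post-capsule administration". The multiple-choice measure is taken once per session (section 4a, Multiple-Choice Procedure).

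The only text on excluding data is in section 4a (Dietary restrictions), where data from non-compliant subjects may be left out. No threshold or timing is given. The other relevant provisions are operational:
- "Paper forms of surveys will be provided as a back-up in the event of technical issues with administering surveys via Qualtrics" (section 4a).
- Extra sessions where needed, with procedural or computer error given as an example (section 10a).
- Completion bonuses (section 10a).

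No section defines who is analysed or what happens to a missing rating.

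**The concern.** A classical ANOVA with every factor within subjects needs a value in every cell for each person. Standard software therefore deletes the whole person when one cell is empty. The plan does not say this will happen, but it names the method and offers no alternative.

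Two groups are affected. The first is participants who leave after test sessions begin but before all ten placebo and nicotine sessions are done. Someone who finishes one whole phase has given a complete five-dose curve, and none of it is used. The second is completers who miss a post-capsule rating in one of those ten sessions, which is foreseeable because the ratings are collected off site.

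At stake are precision on the dose-by-phase question, the use of ratings already collected and paid for, and a result that describes only people who went through, and fully reported on, every placebo and nicotine session. Without a rule, the choice between collapsing time, imputing and deleting would be made after the data are seen.

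**Working it through.** **Inputs from section 7c.** 36 completers; 60 enrolled; attrition up to 40%; effect size .20 (type not stated, taken as Cohen's f); correlation .5; alpha .05; target power .8; 2 phases, 5 doses, 4 times. Assumed, because the documents do not give them: variance components, the timing of dropout and the missed-survey rate.

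**The plan's own figures.** 36/(1 − .40) = 60 enrolled, as stated. Dropouts at the ceiling: 60 × .40 = 24.

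**Cells needed per person.** Ratings at all four hours: 2 × 5 × 4 = 40. Once-per-session outcomes, or time collapsed: 2 × 5 = 10. The two 300 mg caffeine sessions and the pre-drug ratings are not in this ANOVA.

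**Power for dose by phase, plan's two-group form** (N as the total). Noncentrality 5N f²/(1 − rho), df 4 and 4(N − 2). At N = 36 this is 5 × 36 × .04/.5 = 14.4.

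| Usable cases | 36 | 32 | 31 | 30 | 24 |
|---|---|---|---|---|---|
| Power | .864 | .814 | .799 | .783 | .669 |

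This supports the plan's 36.

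**Power, actual design with each person in both phases.** Noncentrality 10n f²/(1 − rho), df 4 and 4(n − 1). At n = 36 this is 28.8.

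| Usable cases | 36 | 31 | 24 | 17 | 16 |
|---|---|---|---|---|---|
| Power | .995 | .986 | .946 | .825 | .796 |

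**Miss rates that would produce those losses.** With independent misses, the rate leaving u of 36 usable over k cells is 1 − (u/36)^(1/k).
- To reach 31: 0.37% per rating with 40 cells, 1.48% with 10.
- To reach 17: 1.9% with 40 cells, 7.2% with 10.

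If misses cluster within people (assumed correlation .1), the rates to reach 31 rise to 0.95% and 2.12%.

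**Precision recovered by using all observed ratings.** The contrast is 4 mg minus placebo under caffeine maintenance, less the same difference under placebo maintenance. Suppose m dropouts each finish exactly one phase, half in each order, and variances are known. Each contributes one of the two dose differences. The information, in units of one completer, is 36 + (m/2) × r, where r = residual/(participant-by-dose + residual) variance.
- Participant .5, residual .5 (no by-dose variance): r = 1. For m = 12, 36 + 6 = 42.0. For m = 24, 36 + 12 = 48.0.
- Participant .2, by-phase .1, by-dose .2, residual .5: r = .5/.7 = .714. For m = 12, 36 + 4.3 = 40.3. For m = 24, 36 + 8.6 = 44.6.

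A full generalised least squares calculation gives the same values, with or without a period term.

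**Simulation under assumed conditions.** 60 enrolled, about 40% attrition driven by the rating in an active-nicotine session, no true interaction, 1,500 runs, variances estimated by REML. The mixed model's variance was 18% to 19% below complete-case when every dropout had some ratings, and 8% to 12% below when 12 of the 24 left before any session. Complete-case bias was 0.00 to 0.06 SD, at most about a quarter of a standard error, with false-positive rates of 4.7% to 5.9%. When the session that triggered exit went unrecorded, mixed-model bias was +0.058 SD against +0.040 for complete cases.

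**The case against.** Several points on the other side stand.

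- **Scope.** A reader might infer that every dropout, and any completer with one missed survey, is lost. The documents do not support that. Someone who leaves after the ten placebo and nicotine sessions is kept. A missed pre-drug or 300 mg caffeine-session survey costs nothing here. Because at least a week of maintenance precedes testing, some leavers have no ratings to lose. Listwise deletion is an inference from the named method, and time enters only as appropriate, so collapsed scores remain open.
- **Power.** A reader might also infer that five unusable completers leave the trial underpowered. That is true only in the two-group calculation, which the plan itself calls conservative. In the within-subjects design 19 of the 36 could be unusable before power nears .80. Dropouts cost no planned power, since 36 completers are budgeted.
- **Bias.** Sections 4f and 8b let people leave for drug reactions or aversive effects, so missingness may depend on treatment. But sections 6a and 6b describe the doses as well tolerated, the direction is unknown, and simulated bias was small.
- **Existing safeguards.** Paper forms, repeat sessions, bonuses and removal for non-compliance reduce missing ratings, and some survey non-compliance may already sit within the 40% allowance. None of these is an analysis rule.
- **Remedy.** Stating an analysis set and a missing-data rule would close the omission without changing the model. That is fair, but a rule that keeps the complete-case ANOVA as primary still leaves the partial data unused. The objection that one-phase participants bring in period effects is right, so the model needs a period term.

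**Conclusion.** The point holds as a cheap improvement. The plan names a method that ordinarily discards partial records, expects up to 40% attrition and off-site ratings, and gives no rule for either.

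The main harm is lost precision: about 4 to 6 completer-equivalents on the 4 mg contrast if 12 dropouts finish one phase, and about 9 to 12 in the optimistic case that all 24 do. These figures rest on assumed variance components and on dropout split equally by order. The gain shrinks as more people leave before any test session. Power loss is material only in the conservative two-group form. How many completers would be dropped cannot be stated, because the documents give no missed-survey rate. Neither a materially biased result nor an underpowered trial is established.

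**What to change.** In section 7c, make the primary analysis a linear mixed model (REML, small-sample degrees of freedom) on all observed post-capsule ratings from the placebo and nicotine sessions.

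- **Analysis set:** every enrolled participant with at least one such session, subject to the section 4a non-compliance exclusion, which should be defined and applied before unblinding.
- **Fixed effects:** phase, dose, time where applicable, their interactions, and period (phase order), because one-phase participants are included.
- **Covariance:** name a participant-level structure and a fallback if it cannot be estimated.
- **Keep:** 36 completers as the recruitment target, and the complete-case repeated measures ANOVA as a sensitivity analysis.
- **Report:** attrition by reason, phase and order.

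The cost is revised wording and a little more analysis work, with no extra participants, visits or data. The downsides are that a covariance structure must be specified and that the model relies on data being missing at random. It does not remove bias if the session that triggered exit goes unrecorded, and people who leave before any test session stay unused under either method.
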